#### 7.9 Database Lock and Unblinding

Once the database has been locked, randomized treatment assignments will be obtained from the TEMPO system following standard procedures. These treatment assignments will then be incorporated into the analysis datasets, tables, listings, and figures.

## 8 STUDY POPULATION

Unless otherwise noted, the Randomized population will be used for listings and summaries of overall study.

## 8.1 Analysis Populations

The analysis population listing will include, for each population detailed in Section 5, whether or not the subject was included in the population and the reason for being excluded from the population. Number of subjects in each analysis population will be summarized overall and by treatment group.

#### 8.2 Subject Enrollment and Randomization

The dates and times of informed consent, whether informed assent by the minor subject is required, and date and time of informed assent, will be listed for all enrolled subjects.

Subject eligibility for randomization, whether subject proceeded to randomization, randomized treatment group, and reason subject not randomized (if applicable), will similarly be listed for all enrolled subjects.

#### 8.3 Inclusion/Exclusion Criteria

Inclusion and exclusion criteria responses will be summarized in a data listing that displays whether all eligibility criteria were met, and what inclusion/exclusion criteria were not met. This listing will be presented for all enrolled subjects.

## 8.4 Subject Disposition

Subject disposition will be recorded in the eCRF, either at the final follow-up visit or when a subject discontinues the study or is lost to follow-up. The number of subjects who enroll, complete the study, discontinue from the study, and reasons for study discontinuation will be summarized.

Number of days on study is calculated as (date of discontinuation – first dose date + 1) for subjects who discontinue the study, and (last study visit date – first dose date + 1) for subjects who complete the study. The number of days on study will be summarized for subjects who were lost to follow up.

## 8.5 Protocol Deviations/Violations

Major and minor protocol deviations will be recorded in the TEMPO system. The following categories of deviations will be recorded:

- Subject did not satisfy the entry criteria
- Subject developed withdrawal criteria during the trial and was not withdrawn
- Subject dispensed wrong treatment
- Subject dispensed incorrect dose
- Subject received prohibited medication
- Subject non-compliance
- Ad libitum peanut consumption
- Other (with free text field to record details).

These protocol deviations will be reviewed in blinded fashion prior to database lock, as described in Section 12, and their categorization as major or minor will be determined prior to database lock.

All protocol deviations will be listed by subject. Major protocol deviations will be summarized by treatment group and overall.

## 8.6 Demographic and Other Baseline Characteristics

Demographic information, in addition to the MTDs of peanut and placebo at the Screening DBPCFC, and the presence of dose limiting symptoms and associated dose levels at the Screening DBPCFC, will be listed for all enrolled subjects. The baseline physicians' global assessment of disease activity will also be listed.

Age in years, at Screening, will be calculated using the following SAS formula: AGE=floor(yrdif( birthdate , Informed Consent date , 'AGE'));

Demographic characteristics, including sex, race, ethnicity, age, height, weight and BMI, will be summarized by treatment group and overall. Baseline immunological characteristics (including total IgE, peanut IgE, peanut-specific IgG4, peanut-specific IgE/IgG4 ratio, and results from SPT) as well as maximum tolerated dose of peanut protein at Screening DBPCFC, and baseline global assessment of disease activity per the VAS, will also be summarized by treatment group and overall.

Demographic and baseline characteristics will be summarized by baseline peanut specific IgE level (less than or equal to 15 kU/L versus greater than or equal to 15 kU/L). Similarly, demographic and baseline characteristics will be summarized by baseline SPT peanut wheal size (less than 8 mm versus greater than or equal to 8 mm).

## 8.7 Allergy History

Allergy history will be listed by subject. The months since most recent anaphylactic reaction to peanut, and months since most recent reaction to peanut that was treated with therapy (if no therapy for most recent anaphylactic reaction to peanut) will be calculated as the difference between the reported date of the reaction and the informed consent date, in months, using the SAS formula:

INTCK('month', date of reaction, informed consent date, 'C')

The duration of peanut allergy (in months), number of anaphylactic reactions to peanut in lifetime (if any experienced), months since most recent anaphylactic reaction to peanut, and months since most recent reaction to peanut that was treated with a therapy will be summarized continuously by treatment group and overall. Types of other allergic conditions the subject has or has had (whether the subject has experienced anaphylactic reactions to peanuts during his lifetime, the therapies administered for the most recent anaphylactic reaction to peanut, and the symptoms experienced during the most recent peanut exposure) will be summarized categorically by treatment group and overall.

#### 8.8 Diet and Non-Peanut Allergy History

All diet and non-peanut allergy history will be listed by subject. The presence of diet and non-peanut allergy history will also be summarized by treatment group and overall.

#### 8.9 Other Medical History

Medical history will be listed by subject and body system.

## 8.10 Subject Progress , Unscheduled Visits and Phone Calls

Subject progression through the study will be displayed in a listing of dates for each scheduled study visit. The unscheduled visit listing will include the date of the visit, the reason for the repeat visit (if applicable), and the types of assessments done.

Telephone calls to assess compliance and symptoms, as displayed in Table 3.5, will also be listed by subject.

#### 9 EFFICACY ANALYSES

The ITT Population will be used for summaries and analyses of the efficacy parameters described below. The mITT and PP Populations will be used where indicated.

Screening and Exit DBPCFC food challenge results will be listed by subject and visit, with order (first or second) and date for both the peanut and placebo challenges, and time and presence of dose limiting symptoms listed for each individual dose administered.

The peanut MTD at Screening and Exit DBPCFCs, x-fold increase in peanut MTD, escalation failure status, desensitization response status and subcategory, and response subcategory for missed Exit DBPCFC will be listed by subject. DBPCFCs with indeterminate results, as defined in Section 9.2, will be flagged. Dose levels tolerated will be summarized by time point, dose level, food challenge (peanut or placebo), and randomized treatment group and overall.

## 9.1 Primary Efficacy Analysis

The primary endpoint is a desensitization response as determined by tolerating at least 300 mg (443 mg cumulative) of peanut protein at the Exit DBPCFC with no more than mild symptoms. Subjects who do not have an Exit DBPCFC will be assigned to a category of responder or non-responder according to Tables 7.1 and 7.2.

The number and percent of subjects with a desensitization response will be reported by treatment group. The desensitization response rate and its 95% confidence interval will be calculated for each treatment group with Wilson (score) confidence limits for the binomial proportion. The 95% confidence interval for the treatment difference (CPNA desensitization rate minus placebo desensitization rate) will be based on Newcombe confidence limits for the difference in binomial proportions. The number and percent of subjects in each response category and subcategory will also be summarized by treatment group.

The primary efficacy analysis will test for a higher desensitization response rate in CPNA versus placebo using the Pearson chi-square statistic in the ITT Population. If any of the expected cell counts are less than 5 (or greater than n-5), Fisher's exact test will be used and exact confidence intervals will be constructed. In this case: (1) exact Clopper Pearson confidence limits will be used for the binomial proportion and (2) exact unconditional confidence limits based on the score statistic will be used for the difference in proportions.

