#### 4 SAMPLE SIZE CONSIDERATIONS

Sample size calculations are based on the primary efficacy analysis of the desensitization response rate. A true placebo response rate of 25% or less among subjects who undergo the Exit DBPCFC is assumed. Those individuals who fail to achieve the daily dose target or withdraw prematurely will be treated as non-responders. This study will enroll approximately 50 subjects randomly assigned in a 1:1 ratio of active to placebo.

If 3 subjects in each arm (about 12%) do not undergo the Exit DBPCFC, then the effective placebo response rate in the ITT analysis is assumed to be 22% or less. With a 2-tailed (alpha=0.05) test, there is at least 80% power to detect an effective CPNA response rate of 58.7 % or more, which corresponds to a CPNA response rate of 66.7% or more among those who undergo the Exit DBPCFC.

If 5 subjects in each arm (about 20%) do not undergo the Exit DBPCFC, then the effective placebo response rate in the ITT analysis is assumed to be 20% or less. With a 2-tailed (alpha=0.05) test, there is at least 80% power to detect an effective CPNA response rate of 56.6% or more, which corresponds to a CPNA response rate of 70.75% or more among those who undergo the Exit DBPCFC.

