## 9.3.1 Maximum Tolerated Dose at Exit DBPCFC

The Exit DBPCFC uses a modified PRACTALL dosing regimen. PRACTALL doses are approximately on a logarithmic scale (3 mg, 10 mg, 30 mg, 100 mg, 300 mg). The highest dose level, 600 mg, was chosen in lieu of the 1000 mg dose level from the PRACTALL guidance to further insure safety. Each single PRACTALL dose step corresponds to a 3 to 3.33-fold (roughly 3.16-fold) increase in dose or a 0.477 to 0.523 (roughly 0.5) increase in the log10 scale. The 600 mg dose level is 2-fold increase in dose or approximately a 0.3 increase in the log10 scale above the 300 mg dose. Each increase of 2 PRACTALL dose steps (e.g. 30 to 300 mg or 10 to 100 mg) corresponds to a 10-fold increase in dose or an increase of 1 unit in the log10 scale. Subjects that cannot tolerate the lowest Exit DBPCFC dose will be set to 0.3 mg (a 1 unit decrease from the 3 mg dose, on the log10 scale) for purposes of analysis to allow for the logarithmic transformation. The MTD for the Exit DBPCFC will be imputed using the rules in Section 7.3 for all subjects with a missing Exit DBPCFC.

Estimates for the probability of tolerating each dose or higher will be based on the discrete hazards model with terms for treatment group effect and the MTD at the Screening DBPCFC (baseline) in the log10 scale. The extreme value hazard function will be used for the model. The probability estimates will be tabulated by treatment group and adjusted for the MTD at baseline. The adjusted probability estimates will be calculated at the median of the MTD at baseline. The adjusted probability estimates will also be plotted. An unadjusted probability estimate will also be calculated by removing the MTD at baseline term from the model. All subjects in the analysis population are considered eligible for the 1 mg dose. Subjects who did not receive the optional 1 mg dose at the Exit DBPCFC will be considered to have successfully passed that dose level and be eligible for the 3 mg dose level.

The treatment group effect will be assessed using the model with both terms to adjust for the MTD at baseline. The hazard ratio for the treatment group effect with its 95% confidence interval and the p-value will be based on the Wald statistic.

The maximum symptom severity at each dose level, and the cumulative maximum severity at each dose level, will be summarized by treatment group.

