## 9.3.2 Change from Baseline in MTD at Exit DBPCFC

Summary statistics will be reported for Screening DBPCFC (baseline), Exit DBPCFC, and change in MTD for the DBPCFC in the  $log_{10}$  dose scale. Results in the  $log_{10}$  scale will be transformed back to the original scale to also report summary statistics in the original scale. Frequencies and percent of subjects will also be presented for each MTD level at the Screening and Exit DBPCFC. Similarly, frequencies and percent of subjects will be presented for all possible ratios (X-fold increase) of the MTD at the Exit DBPCFC relative to baseline.

Analyses of change from baseline MTD will be performed using change calculated on the log10 scale. An analysis of covariance (ANCOVA) model of change from baseline MTD at Exit DBPCFC ( $log_{10}$  mg) will be fit with terms for treatment group and the MTD at baseline ( $\log_{10}$  mg). The baseline adjusted least squares means with 95% confidence intervals by treatment group and for the treatment group difference will be tabulated. The p-value is based on the F-test for treatment group effect adjusted for the MTD at baseline (log10 mg). The ANCOVA model will also be assessed for unequal slopes by adding a term for the treatment group by baseline interaction and using an F-test to test for unequal slopes. If there is a signal of unequal slopes at the 0.10 significance level, then the least squares means with 95% confidence interval, and p-value for the F-test of the treatment group difference will be calculated and reported at baseline MTDs of 1 mg, 3 mg, 10 mg, and 30 mg. P-values and confidence intervals are based on the normality assumption. Residuals for ANCOVA will be assessed for non-normality using the Shapiro-Wilk test. If significant at the 0.05 level, then the Wilcoxon rank sum statistic will be used to test for a treatment group difference to examine the robustness of the ANCOVA F-test. Further exploration may be warranted if unequal slopes are noted.

Least squares mean statistics (point estimates and confidence intervals) from the ANCOVA analysis of change from baseline analysis in the log10 scale will be transformed back to the original scale to obtain geometric least squares mean statistics by treatment group of the ratio of the MTD at the Exit DBPCFC to baseline.

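### The primary test is valid but ignores Screening MTD, which both key secondary tests adjust for; adjusting would change power by about -2 to +9 points, depending on an association the documents do not quantify

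*SAP*

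**What the plan says.** **Primary endpoint.** SAP 9.1 compares response rates "using the Pearson chi-square statistic in the ITT Population", switching to Fisher's exact test when an expected count is below 5. Protocol 9.1.1 also specifies a chi-square test at the 0.05 level. Neither includes a covariate. The sensitivity analyses in SAP 9.2 change only which subjects are included.

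**Key secondary endpoints.** For MTD at the exit challenge, SAP 9.3.1 states: "The treatment group effect will be assessed using the model with both terms to adjust for the MTD at baseline". For change in MTD, the ANCOVA in SAP 9.3.2 is "fit with terms for treatment group and the MTD at baseline". Both are tested only if the primary test is significant (SAP 9.3).

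**Randomization.** SAP 7.8 describes a central schedule of permuted blocks and names no stratification factor.

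**Exploratory.** SAP 9.5 lists log10 Screening MTD first among its potentially prognostic factors. SAP 9.5.1 fits a logistic model of response on treatment and each factor, with and without the interaction.

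**Power.** SAP 4: "With a 2-tailed (alpha=0.05) test, there is at least 80% power to detect" the stated difference. In the first scenario "the effective placebo response rate in the ITT analysis is assumed to be 22% or less", against an "effective CPNA response rate of 58.7 % or more". In the second, "the effective placebo response rate in the ITT analysis is assumed to be 20% or less", against an "effective CPNA response rate of 56.6% or more".

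**The concern.** Screening MTD is the baseline result of the same kind of challenge that defines the primary endpoint. A subject who tolerates 30 mg at screening plausibly has less far to go to tolerate 300 mg at exit than one who tolerates 1 mg. The sponsor's own models for both key secondary endpoints treat it as the covariate to adjust for.

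With about 50 subjects and no stated stratification, the arms can differ in baseline reactivity by chance. The unadjusted test cannot correct for that, and it uses none of the precision the covariate may carry. Planned power only just reaches 80%, and failure of the primary test ends confirmatory testing of both key secondary endpoints. The question is how much power is at issue, and in which direction.

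**Working it through.** **1. Inputs from the documents.** Two-sided alpha 0.05, and about 50 subjects randomized 1:1, so 25 per arm (SAP 4). With 3 per arm not challenged, the ITT rates are 0.25 × 22/25 = 22% and 0.667 × 22/25 = 58.7%. With 5 per arm not challenged, they are 0.25 × 20/25 = 20% and 0.7075 × 20/25 = 56.6%.

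**2. The plan's own figure.** Let a and b be the responder counts and p = (a+b)/50. Pearson rejects when |a-b|/25 ÷ √(p(1-p)·2/25) > 1.96. Summing the two Binomial(25) distributions over the rejection region gives power of 80.0% (58.7% vs 22%) and 80.2% (56.6% vs 20%). The SAP's Fisher fallback leaves both unchanged to that precision. The stated 80% is reproduced.

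**3. Assumptions the documents do not supply.** The Screening MTD mix is taken as 0.3/1/3/10/30 mg in 5/10/25/30/30% of subjects. Eligibility requires dose-limiting symptoms at or before 100 mg, so 30 mg is the highest possible value. Response follows logit P = α(arm) + β·log10 MTD, where β is the log odds ratio (OR) per 10-fold MTD. Each α is set so that the marginal rates stay at 58.7% and 22%.

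**4. Comparison.** The Pearson/Fisher rule is set against the score test for treatment. The score is U = Σ T(y - m), where T is the treatment indicator and m is fitted from log10 MTD alone. The test rejects when |U|/√Var(U) > 1.96. There are 20,000 trials per row, so the Monte Carlo standard error is √(0.8 × 0.2/20,000), about 0.3 points.

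| OR per 10-fold MTD | Pearson/Fisher | Adjusted score | Change (points) |
|---|---|---|---|
| 1 | 80.3% | 78.5% | -1.8 |
| 2 | 80.2% | 79.4% | -0.8 |
| 3 | 80.1% | 80.8% | +0.7 |
| 4 | 79.7% | 81.9% | +2.2 |
| 8 | 79.8% | 85.4% | +5.6 |
| 16 | 80.1% | 89.1% | +9.0 |

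Break-even lies at an OR of about 2.5 to 3. Simulated size under the null is 4.9 to 5.4% for Pearson/Fisher and 5.2 to 5.9% for the adjusted test, so a difference in alpha explains little of the larger gains. Separate runs of 40,000 trials agreed within about half a point.

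**5. A different mix.** With 1, 3, 10 and 30 mg equally likely and the OR expressed per SD of log10 MTD, the change is -1.5 to -1.8 points at OR 1, about 0 at 1.65, +1.5 to +1.7 at 2.0 and +8.8 to +9.1 at 4.1. In the step 3 mix the SD of log10 MTD is 0.571, so 4 per 10-fold is 4^0.571 = 2.2 per SD and 16 is 4.9 per SD. The two sets tell the same story.

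**6. Why a large-sample formula is too generous.** If the covariate explains a share R² of within-arm outcome variance, power becomes Φ(2.80/√(1-R²) - 1.96), starting from 80%. At R² = 0.05 this is Φ(2.874 - 1.960) = 82.0%. At R² = 0.20 it is Φ(3.132 - 1.960) = 87.9%. In simulation at 25 per arm, R² near 0.05 yields a gain of about zero, because estimating the slope has a cost in a small sample.

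**7. Chance imbalance.** In about one trial in six, mean log10 Screening MTD is more than one standard error lower in the CPNA arm. In those trials Pearson power is about 63% at OR 4 and 57% at OR 8, while the adjusted test keeps about 80% and 84%. When the imbalance favours CPNA, Pearson rises to about 91% and 95%, against 81% and 85% adjusted. Under the null at OR 8, Pearson's size in imbalanced trials is about 7 to 8%, against about 5 to 6% adjusted.

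**The case against.** The strongest case for the plan has four parts.

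**The test is not wrong.** Pearson's test needs no covariate for validity, is the test the protocol names, and delivers the stated power. Adjusting an MTD-scale outcome for its own baseline while testing a binary endpoint unadjusted is not a contradiction. All of this stands. The conditional size in step 7 does not make the test invalid, because size averaged over randomizations is close to 5%.

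**The gain is conditional.** A reader might infer that the plan forfeits 2 to 9 points whenever Screening MTD predicts response. The documents do not support that: they give no estimate of the association, and weak prediction yields a small loss. A gain of 2 points needs an OR of about 4. A gain of 9 needs 16, which in the assumed mix means CPNA response of 13% at 1 mg and 90% at 30 mg. The cap at 30 mg, and counting dropouts as non-responders, may both weaken the link. This stands and limits the claim.

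**An adjusted analysis is already planned.** A reader might infer that the SAP never adjusts this endpoint for Screening MTD. It does, in SAP 9.5.1, and SAP 8.6 tabulates Screening MTD by arm. But that model is one of a dozen exploratory ones and cannot settle a primary result challenged because of baseline imbalance.

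**The covariate is not fully defined.** SAP 7.3 recognises only 3, 10, 30 and 100 mg as standard screening doses, yet SAP 9.3.2 reports results at a baseline of 1 mg. The 0.3 mg substitution in SAP 9.3.1 covers only the exit challenge. No log10 value exists for a subject who tolerated no screening dose. This stands, but both key secondary models need the same definition anyway.

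**Conclusion.** The point holds as an efficiency and robustness recommendation. At 25 per arm and 58.7% vs 22%, replacing the unadjusted test with one adjusted for log10 Screening MTD changes power by about -2 points (no association) to +9 points (OR 16 per 10-fold), with break-even at an OR of about 2.5 to 3. The range rests on an assumed Screening MTD mix, a common slope in both arms, and an association strength that the documents leave open.

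The case for changing is the asymmetry: at most about 2 points of average power lost, up to 9 gained, and protection against chance imbalance in baseline reactivity if Screening MTD is prognostic, as the sponsor's own secondary models suppose.

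**What to change.** Before database lock and unblinding:

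- In SAP 9.1, make the primary test the score test for treatment in a logistic model with one linear term for log10 Screening MTD.
- Report the standardized risk difference with its 95% CI, so that the effect stays on the scale of the planned difference in proportions.
- Keep the Pearson/Fisher analysis as the sensitivity analysis, and as the fallback if the model does not converge.
- State the log10 value for subjects who tolerated no screening dose (for example, extend the 0.3 mg convention of SAP 9.3.1), and say how a tolerated optional 1 mg dose is handled. Use the same rule in SAP 9.3.1 and 9.3.2.
- Align protocol 9.1.1.

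**Cost.** About 1 to 2 points of power if Screening MTD is unrelated or only weakly related to response. No new data are needed. The protocol change is more than SAP wording: protocol 11.1 requires sponsor, DMC and IRB approval and submission to FDA. Subjects are unblinded individually at exit (SAP 7.8), and some sponsor representatives can see ARC002 assignments (SAP 7.7). The decision should therefore be made and documented by people without access to those assignments. If the protocol cannot be amended, moving the main-effect model from SAP 9.5.1 to SAP 9.2 as a named sensitivity analysis would address imbalance but add no power to the primary test.
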